1. PROTOCOL SYNOPSIS

A Phase 2, Randomized, Double-Blind, Placebo-controlled Study of the Safety and Efficacy of STI-5656 (Abivertinib Maleate) in Subjects Hospitalized Due to COVID-19

Protocol Number: STI-5656-2001, Version 4.0

Investigator(s)/ Study Centers

This study will be conducted at multiple study centers located in the United States.

Phase: 2

Objectives

Primary Objective:

- To assess the efficacy of STI-5656 in subjects with severe coronavirus disease 2019 (COVID-19)

Secondary Objectives:

- To assess the safety and tolerability of STI-5656 in subjects with severe COVID-19
- To assess the pharmacokinetic profile in the study population

Endpoints

Primary Endpoint:

- Proportion of subject alive and free of respiratory failure at Day 28

Respiratory failure, is defined based on resource utilization of any of the following modalities:

- Noninvasive positive pressure ventilation or continuous positive airway pressure
- Endotracheal intubation and mechanical ventilation
- Oxygen delivered by high-flow nasal cannula (heated, humidified, oxygen delivered via reinforced nasal cannula at flow rates >20 L/min with fraction of delivered oxygen ≥ 0.5)
- Extracorporeal membrane oxygenation (ECMO)

Secondary Endpoints:

- Types, frequencies, and severities of adverse events (AEs) and the relationships of AEs to IP; includes serious adverse events (SAEs)
- Proportion of subjects alive and free of respiratory failure at Day 60
- Change in clinical status (on a 0-8-point ordinal scale)¹ of subject at Day 7, Day 14 and Day 28

¹ 8-category ordinal scale of patient health status ranges: 0=no clinical or virological evidence of infection; 1=no limitation of activities; 2=limitation of activities; 3=hospitalized, no oxygen therapy; 4=oxygen by mask or nasal prongs; 5=non-invasive ventilation or high-flow oxygen; 6=intubation and mechanical ventilation; 7=ventilation + additional organ support – pressors, rapid response team (RRT), extracorporeal membrane oxygenation (ECMO); 8=death. See [Section 14.2](#) for form.

- Proportion of subjects alive and discharged from Intensive Care Units (ICU) at Days 14 and 28
- Time from randomization to first occurrence of respiratory failure or death on study due to any cause up to Day 28
- Percent change from baseline in CRP at Days 3, 5, 7, 10, 14, 28
- Relative change from baseline in oxygenation index (PaO₂/FiO₂) up to Day 5
- All-cause mortality at Day 60 and Day 90
- Number of days alive and free of respiratory failure at Day 28
- Number of days with respiratory failure up to Day 28
- Number of days hospitalized up to Day 28
- Number of days in ICU (length of stay) up to Day 90
- Number of days alive outside of hospital up to Day 28
- Number of days alive outside of hospital up to Day 90
- Pharmacokinetics in the study population at 100 mg QD

Exploratory Endpoints:

- See [Section 3.2.3](#)

Subject Population

- ≥18 years with reverse transcriptase polymerase chain reaction (RT-PCR) confirmed infection with severe acute respiratory syndrome coronavirus 2 (SARS-CoV-2)
- COVID-19 pneumonia (documented radiographically) requiring hospitalization; oxygen saturation level <94% on room air or subject requires supplemental oxygen.

Refer to [Section 5](#) for complete eligibility details.

Investigational Product (IP) Description:

Investigational Product (IP) is STI-5656 (Abivertinib maleate)

Planned Sample Size

Approximately 80 subjects will be enrolled in this study, 40 will be randomized to each of two treatment arms.

Treatment Arms

All subjects will receive current standard of care (SOC) treatments.

In this setting, subjects will receive one of two treatments up to Day 14 or until hospital discharge (if sooner):

Arm 1: STI-5656 (100 mg QD starting dose)

Arm 2: Placebo QD

Duration of Study

For subjects, the total duration of the study will be up to 94 days (up to 4 days for the screening period plus up to 14 days for treatment and up to 90 days from randomization for follow-up).

The length of the study will be approximately 7 months (4 months for enrollment plus up to 90 days study duration).

Study Design

This is a Phase 2, randomized, double blind, placebo-controlled, 2-arm multicenter study to assess the safety and efficacy of STI-5656 (capsule administered orally) in the setting of current standard of care (SOC) in subjects with RT-PCR confirmed SARS-CoV-2 (COVID-19) infection and pneumonia (documented radiographically) requiring hospitalization. Subjects must have oxygen saturation levels < 94% on room air or subject requires supplemental oxygen.

Eighty (80) subjects meeting eligibility criteria will receive SOC treatment and will be randomized at a 1:1 ratio to one of two treatment arms

- Arm 1: STI-5656
- Arm 2: Placebo

The starting dose of STI-5656 is 100 mg PO QD administered up to 14 days or until hospital discharge whichever is sooner. Placebo follows the same schedule.

Subjects who discontinue at any time after randomization will not be replaced. There is no treatment crossover in this study.

Once subjects provide informed consent, they will have screening assessments performed (up to a 7-day screening window). Study Day 1 is the day of randomization. Subjects randomized should receive their first dose of STI-5656 or placebo on the day they are randomized (Day 1).

Subjects will be assessed daily while hospitalized. Subjects in both arms are assessed for adverse events and toxicities and all adverse events should be reported regardless of treatment arm assignment or causality.

PK samples will be collected from the first 20 subjects enrolled in this trial. For sampling time points please refer to the schedule of assessments.

Subjects will have an outpatient visit on Day 28 (for various study procedures) and a telephonic contact on Day 60 to collect any additional AEs and follow-up for unresolved AEs to resolution or to establishment of a new baseline.

SOC treatments will be collected in the electronic case report form (e-CRF) until hospital discharge. Continued outpatient treatment (concomitant medications) will be collected until Day 28. Any investigational medication received will be collected until Day 90.

Note: Investigational medicines other than STI-5656 are prohibited up to Day 28 or hospital discharge.

Discharged subjects will be contacted at Day 60 and Day 90 to collect survival, any experimental treatments and additional hospitalization information since the study hospital discharge.

[figure not shown]
Subjects should be encouraged to remain in the study even if Study Drug is discontinued (for any reason).

Statistical Design

An evaluable sample size of 40 subjects per group (treatment arm) will provide 80% power ($\alpha=0.05$, 2-sided) to detect a difference between groups in the number of subjects alive and free of respiratory failure at Day 28. This assumes that 95.7% of subjects who received STI-5656 plus SOC (group 1) and 70% of subjects who received only SOC (group 2) will be alive and free of respiratory failure at Day 28. This represents a treatment effect difference of approximately 26%.

All tests of significance will be assessed at alpha level=0.05, 2-sided.

Figure 1: Study Design

Schedule of Assessments (SOA)

See [Table 1](#) for SOA

Data Monitoring Committee

An independent data monitoring committee (DMC) will be established under a charter for the trial and tasked to evaluate data from the study to ensure the ongoing safety of the study subjects and make recommendations to the Sponsor concerning safety and trial conduct. A blinded independent statistician will be used to facilitate DMC support. This statistician will have no role in the statistical assessments conducted for the study at its conclusion. Discussions with the independent statistician will be conducted during a closed session during the DMC deliberations. Sponsor, CRO and study site personnel will only participate in the open session. Unblinding of a given subject to assess an AE stopping rule trigger will be handled in a way to keep the Sponsor, CRO (and staff) and study site personnel blinded.

A futility analysis will be performed by an independent biostatistician after the first 40 subjects are enrolled.

Additional details may be found in the Statistical Analysis Plan (SAP) for this study.

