9. STATISTICS

9.1. Statistical Considerations

All tests of significance will be assessed at alpha level=0.05, 2-sided. All analyses and data presentations will be generated using SAS version 9.4, or higher (Cary, NC).

Subjects who are randomized to the study and discontinue before the end of the study will not be replaced. Missing values will not be imputed. For success/failure endpoints, subjects who discontinue prior to the specified time point will be included in the analysis as treatment failures and censored at the last day of follow-up for the time-to-event analysis. For all other endpoints, the mixed effect model repeat measurement (MMRM) analysis will be employed. The MMRM analysis only includes the available data. It has been demonstrated that the MMRM approach leads to estimators with comparatively small bias, and controls Type I error rates at a nominal level in the presence of missing completely at random (MCAR) or missing at random (MAR) and some possibility of missing not at random (MNAR) data (see <https://pubmed.ncbi.nlm.nih.gov/19212876/>).

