9.2. Sample Size Estimation

An evaluable sample size of 40 subjects per group will provide 80% power (alpha=0.05, 2-sided) to detect a difference between groups in the number of subjects alive and free of respiratory failure at Day 28. This assumes that 95.7% of subjects who received STI-5656 plus SOC and 70% of subjects who received placebo plus SOC only will be alive and free of respiratory failure at Day 28. This represents a treatment effect difference of approximately 26%.

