9.4.3. Primary Endpoints

For the primary endpoint, the proportion of subjects alive and free of respiratory failure at Day 28, the number and percentage of subjects will be presented by group. Possible differences between groups will be assessed using a generalized linear mixed model, assuming a binomial distribution and a logit link. The model will include group as a fixed effect. Subjects who discontinue the study prior to Day 28 will be considered treatment failures.

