### 7.4 Interim Analysis

A non-binding interim futility analysis will be performed after 40 subjects have reached the study primary endpoint. The analysis will be performed by an independent biostatistician who will have no contact with the study team.

This interim analysis will use non-binding futility boundaries. At 50% planned subjects (40 subjects out of 80 subjects total), futility interim will be performed. O'Brien-Fleming beta spending function will be used. Futility bound on Z scale is 0.537. The futility bound is crossed if an observed Z statistic is less than 0.537. Nominal beta is 0.296 with cumulative beta being 0.065 at the interim and 0.192 at the final analysis. The above interim planning was performed under 1-sided test setting using nQuery Version 8.6.1.0. Using 1-sided alpha of 0.025, with

continuity correction, sample size of 40 per group (80 total) have 80.8% power (beta 0.192) to detect the difference of 95.7% in active arm vs 70% in control arm.

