## **9.0 EFFICACY EVALUATION**

### **9.1 Primary Endpoint**

The primary efficacy endpoint is the proportion of subjects alive and free of respiratory failure at Day 28, where respiratory failure, is defined based on resource utilization of any of the following modalities:

- Noninvasive positive pressure ventilation or continuous positive airway pressure
- Endotracheal intubation and mechanical ventilation
- Oxygen delivered by high-flow nasal cannula (heated, humidified, oxygen delivered via reinforced nasal cannula at flow rates  $>20$  L/min with fraction of delivered oxygen  $\geq 0.5$ )
- Extracorporeal membrane oxygenation

The number and percentage of subjects will be presented by treatment group using FAS population. Primary analysis to evaluate the differences between groups will utilize a

generalized linear mixed model, assuming a binomial distribution and a logit link. The model will include group as a fixed effect. Subjects who discontinue the study prior to Day 28 will be considered treatment failures.

Sensitivity analyses may be performed using PP population.

After 40 subjects have been enrolled and completed Day 28, an interim futility analysis will be performed to examine the proportion of subjects alive and free of respiratory failure at Day 28. The interim analysis is a non-binding analysis. See Section 7.4 for details.

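### The primary comparison has no prespecified between-arm estimate, interval or named test, and its logit model gives no finite odds ratio if no active-arm subject fails

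*Protocol*

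**What the plan says.** **Design scale.** The Protocol Synopsis (Statistical Design), Protocol 9.2 and SAP 5.0 size the trial on two proportions. Protocol 9.2 gives the expected success rates: "This assumes that 95.7% of subjects who received STI-5656 plus SOC and 70% of subjects who received placebo plus SOC only". The Synopsis adds "This represents a treatment effect difference of approximately 26" per cent. With 40 evaluable subjects per group the stated power is 80%. SAP 7.4 gives 80.8%, with a continuity correction and a one-sided alpha of 0.025.

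**Analysis scale.** SAP 9.1 presents the number and percentage of successes per arm on the FAS and compares the arms with a "generalized linear mixed model, assuming a binomial distribution and a logit link. The model will include group as a fixed effect". Protocol 9.4.3 matches: "Possible differences between groups will be assessed using a generalized linear mixed model, assuming a binomial distribution and a logit link". Protocol 9.1 sets the level: "All tests of significance will be assessed at alpha level=0.05, 2-sided". SAP 9.2.1 applies the same method to respiratory failure at Day 60, ICU discharge at Days 14 and 28, and mortality at Days 60 and 90.

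**What is absent.** The supplied text of both documents names no difference, odds ratio or confidence interval for these endpoints. It does not say whether the model's test is Wald or likelihood ratio, or what happens if an arm has no failures. SAP 7.2 sets summary statistics and rounding in detail but lists no interval.

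**The concern.** The primary objective is to assess efficacy, and with 80 subjects the precision of the estimated benefit matters as much as the p-value. The plan leaves the effect scale, the interval and the interval method to be chosen after unblinding, which is discretion that a SAP is meant to remove.

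The default output of the chosen model is an odds ratio. The assumed active-arm success rate leaves about two expected failures in 40 (40 × 0.043 = 1.7), so that odds ratio rests on very few events. In the most favourable result, no failures at all, it has no finite value and the plan gives no fallback.

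**Working it through.** **Inputs.** p1 = 0.957, p2 = 0.70, n = 40 per arm, critical value 1.96 (Protocol 9.1, Protocol 9.2, SAP 7.4). The one-sided 0.025 in SAP 7.4 gives the same critical value.

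**1. The plan's own figure.** With mean rate 0.8285:
- SE under the null = √(2 × 0.8285 × 0.1715/40) = 0.0843.
- SE under the alternative = √((0.957 × 0.043 + 0.70 × 0.30)/40) = 0.0792.
- Continuity-corrected power = Φ((0.257 − 1/40 − 1.96 × 0.0843)/0.0792) = Φ(0.843) = 80.0%.

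This agrees with the protocol's 80% and is within a point of the SAP's 80.8%. The trial is sized on a continuity-corrected test of two proportions.

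**2. Estimates near the design.** The control arm is held at 28/40.
- Odds ratio = [x/(40 − x)]/(28/12), with SE of its log = √(1/x + 1/(40 − x) + 1/28 + 1/12).
- The Newcombe limits combine the Wilson limits of each arm; for 28/40 these are 0.5457 and 0.8193.

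| Active successes | Odds ratio (95% CI) | Difference in points (Newcombe 95% CI) |
|---|---|---|
| 37/40 | 5.3 (1.4 to 20.5) | 22.5 (5.3 to 38.7) |
| 38/40 | 8.1 (1.7 to 39.3) | 25.0 (8.4 to 40.8) |
| 39/40 | 16.7 (2.1 to 136) | 27.5 (11.7 to 43.1) |
| 40/40 | infinite | 30.0 (15.2 to 45.4) |

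Example for 38/40, whose Wilson limits are 0.8350 and 0.9862:
- lower = 0.25 − √((0.95 − 0.8350)² + (0.8193 − 0.70)²) = 0.084
- upper = 0.25 + √((0.9862 − 0.95)² + (0.70 − 0.5457)²) = 0.408

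**3. Chance of no active-arm failures.** 0.957^40 = 0.172. At 40/40 the log odds ratio and its standard error both diverge, so a Wald p-value is near 1 however large the observed benefit.

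**4. Does the unnamed test matter?** I summed the binomial probabilities of all 41 × 41 outcomes at the design rates, counting 40/40 as not significant under Wald:

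| Test | Power |
|---|---|
| Wald on log odds ratio | 70.5% |
| Likelihood ratio | 91.5% |
| Pearson (score) | 91.5% |

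**5. Would the interval and the test agree?** By the same sum, the Newcombe interval and the Wald test disagree on significance in 20.5% of trials: 17.2 points from 40/40 and 3.3 from other outcomes. Against the likelihood-ratio or score test, the disagreement is 0.5%.

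**The case against.** A reader might infer that the result cannot be set against the design effect at all, or that the trial will report only a p-value and an unstable odds ratio. The documents do not support either. SAP 9.1 reports the count and percentage per arm, so the difference follows by subtraction, and anyone can compute an interval from the four counts. With group as the only stated term, the model's fitted probabilities equal the observed proportions.

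Nor is it an error to size a trial on a difference and test with a logit model, since both test the same null of equal proportions. The documents do not declare the risk difference to be the effect measure, and the supplied text ties no development decision to an absolute benefit. Choosing that scale is partly a matter of judgement.

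The table also compares unlike scales. On the log scale the odds ratio moves from 1.67 to 2.82, with standard errors of 0.69 to 1.07. The difference rests on the same few failures, and its interval is still about 32 points wide at 38/40. The fact that one odds ratio means different absolute benefits at different control rates carries little weight, because the control rate is reported.

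All of this stands, and it narrows the point without removing it. The interval, its method, the test and the no-failure case remain unspecified, and the last two can change the primary conclusion. Adding an interval while leaving the test open would create its own conflict, as step 5 shows.

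**Conclusion.** The gap is one of prespecification. It does not invalidate the test in principle. The estimate can be recovered by subtraction, but its interval and method are not fixed in advance. The odds ratio that the model naturally yields is unstable near 96% success and has no finite value in about one trial in six at the sponsor's own assumption. Depending on which unnamed test is used, power at the design rates runs from 70.5% to 91.5%. The change should be made before unblinding.

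The figures assume the design rates, 40 analysed subjects per arm with no dropout, no random effect in the primary model (none is named) and a normal reference for Wald. They ignore the non-binding futility look. Discontinuations count as failures, so any in the active arm would make 40/40 less likely than 17%.

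**What to change.** In SAP 9.1, and for the binary endpoints in SAP 9.2.1:

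1. Prespecify the difference in proportions, STI-5656 minus placebo on the FAS, with a two-sided 95% Newcombe or Miettinen-Nurminen interval (one of them named), as the primary effect estimate.
2. Name the test taken from the logit model, and a fallback when an arm has no failures. A likelihood-ratio or score test, rather than Wald, serves both purposes.
3. State that this test governs the significance claim and that the interval is for estimation.

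No change to sample size or data collection is needed. SAP 1.0 says that the SAP supersedes the protocol's analysis description, so no protocol edit is needed either. The cost is SAP wording and a line of output per binary endpoint. The small downside is that two effect scales appear side by side, and the interval and test can occasionally disagree (0.5% of trials at the design rates with Newcombe and a likelihood-ratio or score test).

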2. SCHEDULE OF ASSESSMENTS (SOA)

Table 1: Schedule of Assessments

Assessments	Screening (Day -4 to -1)	Day 1 (Dose 1) ¹	Daily until hospital discharge	Hospital discharge or Early Term ²	Outpatient visit: Day 28	Telephone Follow-up at Day 60 and 90
Informed Consent	X					
Assess eligibility	X	X				
Demographics ³	X					
RT-PCR assay for SARS-CoV-2 ⁴	X					
Medical history (including COVID-19 history)	X					
Concomitant medications	X	X	X	X	X	
Physical exam, including weight; height ⁵	X			X	X	
Vital signs ⁶	X	X	X	X	X	
12-lead ECG (performed locally) ⁷	X	X				
Pregnancy test for FCBP only ⁸	X	X		X	X	
Urinalysis ⁹	X	X	X		X	
Blood for hematology, coagulation and chemistry ¹⁰	X	X	X	X	X	
Blood for CRP, serum ferritin, VEGF-A and cytokines ¹¹	X	X	X	X	X	
Day 3, 5, 7, 10, 14 and 28 only						
Respiratory Status ¹²	X	X	X	X		
Adverse Events ¹³	X	X	X	X	X	
Assess clinical status ¹⁴	X	X	X	X		
IRT entry (at screening, randomization, then early termination or study completion	X	X		X		X
Study Drug administration (QD p.o.)		X	X ¹⁵			

Assessments	Screening (Day -4 to -1)	Day 1 (Dose 1) ¹	Daily until hospital discharge	Hospital discharge or Early Term ²	Outpatient visit: Day 28	Telephone Follow-up at Day 60 and 90
Sampling for pharmacokinetics ¹⁶	X ¹⁶	X ¹⁶	X ¹⁶			
Survival and additional experimental meds/ hospitalization/ICU status					X	X

Abbreviations: AEs: adverse events; ALC: Absolute lymphocyte count; ALT: alanine aminotransferase; AST: aspartate aminotransferase; CRP: C-reactive protein; BUN: blood urea nitrogen; CMP: complete metabolic panel; COVID-19: Coronavirus Disease 2019; D: day; ECG: electrocardiogram; ECMO: extracorporeal membrane oxygenation; ET: Early Termination; F: Fahrenheit; FCBP: female of childbearing potential; FiO₂: Fraction of inspired oxygen; IRT: Interactive Response Technology; IL: Interleukin; IFN γ : interferon gamma; QD: once daily; PaO₂: partial pressure of oxygen in arterial blood; p.o.: by mouth; RBC: red blood cells; rbc/hpf: red blood cells per high power field; RRT: rapid response team; RT- PCR: Reverse transcription polymerase chain reaction; TNF α : tumor necrosis factor alpha; WBC: white blood cells

¹ All assessments on Day 1 are to be performed prior to first dose of STI-5656. Day 1 laboratory results do not need to be available prior to randomization (and first dose of STI-5656 if assigned to that arm) if lab results are available from the previous 24 hours

² If the subject wishes to discontinue from the study prior to Day 28 or hospital discharge, every effort should be made to perform an Early Termination (ET) Visit within 7 days after the decision to discontinue the study.

³ Demographics includes age, sex, race, ethnicity, date of birth.

⁴ SARS-CoV-24 positive RT-PCR test results received more than 7 days prior to planned randomization may be used to confirm eligibility if the site is unable to obtain a repeat sample and confirm results prior to planned randomization day and if the subject has progressive disease consistent with COVID-19.

⁵ Height at screening only

⁶ Vital signs include body temperature (F), respiratory rate, radial pulse rate, systolic and diastolic blood pressure, and oxygen saturation (pulse oximetry). Pulse and blood pressure should be taken with subject in at least in a semi-recumbent position. It is preferred to collect vital signs approximately mid-afternoon each day. Vital signs may be obtained at additional times as deemed necessary by the Investigator.

⁷ ECG to be performed at Screening, between 2 and 4 hours after study drug dosing, and as clinically indicated.

⁸ Females of childbearing potential must have a negative pregnancy test at screening and within 24 hours before randomization (Day 1) unless the previous negative pregnancy test was within 72 hours of Day 1. Urine pregnancy test is acceptable. The test should be repeated at the time of the Day 28 visit.

⁹ Urinalysis performed locally. Urinalysis includes protein, glucose, and blood (microscopic) – red blood cells per high power field (rbc/hpf).

¹⁰Laboratory tests performed locally.

Hematology: Hemoglobin, hematocrit, red blood cell (RBC) count, RBC indices, mean corpuscular hemoglobin, mean corpuscular hemoglobin concentration, platelet count (or estimate), and white blood cell count including differential.

Coagulation: INR, PTT.

Chemistry: performed locally. 14-analyte complete metabolic panel (CMP) : Albumin, alkaline phosphatase (ALP), alanine aminotransferase (ALT), aspartate aminotransferase (AST), bicarbonate, total bilirubin (TBIL), blood urea nitrogen (BUN), calcium, chloride, creatinine, glucose, potassium, sodium, total protein, D-dimer, fibrinogen.

¹¹Cytokines include TNF α , IFN γ , IL-6, IL-1 β , IL-7, IL-8, IL-10, IL-12, IL-17, IL-18, IP 10, VEGF-A

¹²Record FiO₂ (and PaO₂) at the time of arterial blood gas sampling. If PaO₂ is not available, use SPO₂. Other respiratory status data to collect includes oxygen supplementation status: mechanical ventilation, face mask, nasal cannula or room air. Radiographic findings will also be collected.

¹³AEs will be collected from the time of informed consent to Day 60. Any ongoing AEs at Day 28 will be followed until resolution or stabilization.

¹⁴An 8-category ordinal scale of patient health status ranges: 0=no clinical or virological evidence of infection; 1=no limitation of activities; 2=limitation of activities; 3=hospitalized, no oxygen therapy; 4=oxygen by mask or nasal prongs; 5=non-invasive ventilation or high-flow oxygen; 6=intubation and mechanical ventilation; 7=ventilation + additional organ support – pressors, rapid response team (RRT), extracorporeal membrane oxygenation (ECMO); 8=death. See [Section 14.2](#) for form.

¹⁵STI-5656 or placebo administration up to Day 14 or hospital discharge, whichever is sooner for subjects in Treatment Arm 1. Study drug capsules should be taken orally with 200-250 mL of water following at least 2 hours of fasting.

¹⁶Samples will be collected from the first 20 subjects enrolled. Sampling timepoints are as follows: Day 1 (predose) and at 0.5, 1, 2, 4, 8, 12, postdose on dosing days 1 and 8.

